1. OBJECTIVES

1.1. Primary Objective

1.1.1. Determine the toxicity and safety of incorporating Zydelig into the post- ASCT maintenance setting for iNHL and tiNHL immediately after ASCT. Toxicity will be monitored continuously throughout the trial.

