5. TREATMENT PLAN

5.1 Zydelig Administration

Treatment will be orally administered on an inpatient and outpatient basis with the starting dose of 150 mg by mouth twice a day for continuous 28-day cycles. Treatment will continue until progression, intolerance, or patient/physician discretion to stop therapy. Zydelig will be started with count recovery (ANC over 500 cells/mm³, non-transfused platelet count over 20,000 K/mm³) in patients who are at least 30 days after induction and/or transplant but no more than 120 days post-transplant.

Reported adverse events and potential risks are described in Section 9. Appropriate dose modifications for Zydelig are described in Section 7. No investigational or commercial agents, or therapies other than those described below may be administered with the intent to treat the patient's malignancy.

Patients should swallow Zydelig tablets whole each morning and evening (i.e. every 12 hours). Tablets may be taken with or without food. Patients should keep track of adherence to Zydelig therapy by using the "Patients Drug Diary" (see appendix B). This diary will be collected at the end of each cycle. At the time of collection, the diary will be reviewed by a staff member and the patient will be prompted to complete any blank entries before completion of the visit. Should a patient miss or vomit a dose of Zydelig within less than 6 hours of the planned dose, the patient should take it as soon as possible. Patients who miss or vomit a dose of Zydelig longer than 6 hours after the planned dose should wait until the next scheduled dose to resume taking Zydelig.

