6. REQUIRED DATA/STUDY CALENDAR

Pre-Study Testing Intervals

To be completed within 16 DAYS before study treatment:

- All blood work
- History and physical

To be completed within 28 DAYS before study treatment:

- Any X-ray, scan of any type (e.g., CT or MRI) or ultrasound that is utilized for tumor measurement

To be completed within 42 DAYS before study treatment:

- Any X-ray, scan of any type (e.g., CT or MRI) or ultrasound that is not utilized for tumor measurement
- Bone marrow biopsy and aspirate (unilateral) is required if there washistory of bone marrow involvement.

	Prior to Treatment	Cycle 1 Day 1	Cycle 1 Day 8 ± 3 days	Cycle 1 Day 15 ± 3 days	Day 1 of Each Subsequent Cycle ± 3 days ^l	Cycle 2 Day 15 ± 3 days	Cycle 3 Day 15 ± 3 days	End of Treatment* * ± 3 days	Time of Restaging and Post-treatment Follow-up*, %
Tests & Observations									
History & Progress Note	X	X			X			X	X
Physical Examination	X	X			X			X	X ^j
Pulse, Blood Pressure	X	X			X			X	X
Height	X								
Weight	X	X			X			X	X
Performance Status	X	X			X			X	X
Drug Toxicity Assessment	X	X			X			X	
Solicited Abnormalities/AEs	X	X ^A			X ^A			X	
Laboratory Studies									
CBC, Diff, Platelets	X	X			X			X	X
Serum Creatinine, CrCl (est), BUN	X	X			X			X	X
Serum Electrolytes	X	X			X			X	X
AST, ALT, Alk Phos, Bilirubin	X	X		X	X ^A	X	X	X	X
Uric Acid, Phosphate, LDH	X	X			X			X	X
Blood CMV PCR	X	X			X			X	
Beta2-Microglobulin	X							X	

Serum or Urine BHCg	X ^B							X	
Thyroid Function Tests (T3,T4, TSH)	X ^E				X ^E			X	
Triglycerides	X ^I							X	
HIV~	X ^{C~}							X	
HBsAg~, Anti-HBc~Ab,HepC Ab~	X~							X	
ECG	X		X ^F					X	
Staging									
CT/MRI (chest/abd/pelvis) with Tumor Measurements	X							X	X ^D
CT Neck	X							X	X ^D
PET (or PET/CT)	X							X	X ^D
Bone Marrow Asp & Biopsy	X							X ^G	X ^G
Histologic Review	X							X ^K	
Correlative Samples	X ^H	X ^H						X ^H	X ^H

Table 1

* Restage every 3 cycles during treatment (i.e., cycles 3, 6, 9, 12, etc.), then every 3 months for 1 year, then every 6 months for another year.

** If off study prior to month 12 study treatment

% Starting at cycle 15 through cycle 24: Visit window +/- 4 weeks. Starting at cycle 27 through cycle 36: Visit window +/- 12 weeks.

^ Monitor ALT, AST, Alk Phos and bilirubin in all patients every 2 weeks (or 15 days) for the first 3 cycles of treatment, than every 4 weeks during subsequent cycles.

~ If done before the transplant, no need to repeat them.

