A. Abnormalities/adverse events should be solicited, and severity graded, on day 1 of each cycle of treatment.

B. In women of childbearing potential (as defined in Section 3.1.7). A negative serum or urine HCG test is required within 14 days prior to study.

C. Patients with known HIV positivity are excluded.

D. CT, PET or PET/CT done PRN to follow measurable disease. Scan to be done with or without PET depending on the patient disease status.

- E. Thyroid function tests every 3 cycles while on treatment and at completion of protocol therapy(Prior to treatment, C3D1, C6D1, C9D1, C12D1).
- F. ECG on day 8 of cycle 1, and then as clinically indicated. The steady-state (day 8) ECG is a requirement of the FDA under the Alliance IND for Zydelig.
- G. Repeat bone marrow aspirate and biopsy to confirm CR only if involved at baseline. Also a bone marrow aspirate/biopsy will be done if suspicion of bone marrow involvement.
- H. See protocol 19.2 Time Points of appendix D Correlative Studies
- I. Triglycerides Day 1 of cycles 3, 6, 9, 12 and then every 3 months until month 24. Then again at months 24, 30, & 36.
- J. Physical Exam during follow-up.
- K. Only if there is progression, as judged by the Investigator

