Fatal and/or serious hepatotoxicity occurred in 18% of patients treated with Zydelig monotherapy and 11% of patients treated with Zydelig in combination trials. Elevations in ALT or AST greater than 5 times the upper limit of normal have occurred. These findings were generally observed within the first 12 weeks of treatment and were reversible with dose interruption. After resumption of treatment at a lower dose, 26% of patients had recurrence of ALT and AST elevations. Discontinue Zydelig for recurrent hepatotoxicity. Avoid concurrent use of Zydelig with other drugs that may cause liver toxicity. Monitor ALT and AST in all patients every 2 weeks for the first 3 months of treatment, every 4 weeks for the next 3 months, then every 1 to 3 months thereafter. Monitor weekly for liver toxicity if the ALT or AST rises above 3 times the upper limit of normal until resolved. Withhold Zydelig if the ALT or AST is greater than 5 times the upper limit of normal, and continue to monitor AST, ALT and total bilirubin weekly until the abnormality is resolved.

Severe Diarrhea or Colitis

Severe diarrhea or colitis (Grade 3 or higher) occurred in 14% of patients treated with Zydelig monotherapy and 19% of patients treated with Zydelig in combination trials. Diarrhea can occur at any time. Avoid concurrent use of Zydelig and other drugs that cause diarrhea. Diarrhea due to Zydelig responds poorly to antimotility agents. Median time to resolution ranged between 1 week and 1 month across trials, following interruption of Zydelig therapy and in some instances, use of corticosteroids.

Pneumonitis

Fatal and serious pneumonitis occurred in patients treated with Zydelig. In randomized clinical trials of combination therapies, pneumonitis occurred in 4% of patients treated

with Zydelig compared to 1% on the comparator arms. Time to onset of pneumonitis ranged from <1 to 15 months. Patients taking Zydelig who present with pulmonary symptoms such as cough, dyspnea, hypoxia, interstitial infiltrates on a radiologic exam, or a decline by more than 5% in oxygen saturation should be evaluated for pneumonitis. If pneumonitis is suspected, interrupt Zydelig until the etiology of the pulmonary symptoms has been determined. Patients with pneumonitis thought to be caused by Zydelig have been treated with discontinuation of Zydelig and administration of corticosteroids.

Infections

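### During treatment Table 1 asks about toxicity only on day 1 of each cycle, so a patient who stays on drug is first asked about symptoms 28 days after the first dose, although toxicity is the primary objective

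*Combined protocol and SAP*

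**What the plan says.** Section 1.1 gives one primary objective: "Determine the toxicity and safety of incorporating Zydelig into the post- ASCT maintenance setting for iNHL and tiNHL immediately after ASCT". It adds: "Toxicity will be monitored continuously throughout the trial". Section 14.1 commits to reporting the proportion removed for toxicity together with all toxicities by type and grade. Sections 9.3 and 9.5 require each change of CTCAE grade within an episode to be recorded, and Table 7 asks for start and stop dates.

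The schedule is in section 6. Table 1 has a row for "Drug Toxicity Assessment" and a row for solicited abnormalities and AEs. Both are marked before treatment, at C1D1, on day 1 of each later cycle and at End of Treatment. Footnote A confirms this for the treatment period: "Abnormalities/adverse events should be solicited, and severity graded, on day 1 of each cycle of treatment". The expectedness list in section 9.3 likewise asks for solicitation at baseline and for each cycle.

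The calendar also has four contacts between day-1 visits. C1D8 carries an ECG ("ECG on day 8 of cycle 1, and then as clinically indicated"). C1D15, C2D15 and C3D15 carry the liver panel ("Monitor ALT, AST, Alk Phos and bilirubin in all patients every 2 weeks (or 15 days) for the first 3 cycles of treatment"). Both toxicity rows are blank at all four.

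**The concern.** When the primary result is a description of toxicity, the AE tables are only as good as the questioning behind them. C1D1 is the day of first dose, so the inquiry on that day cannot pick up drug effects. The next scheduled one is C2D1. A symptom that starts, worsens and settles in between has to be rebuilt from memory, including its onset date and each change of grade.

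This matters most for events with no laboratory marker. Table 3 classes diarrhea by stools per day over baseline and pneumonitis by whether it is symptomatic; the day 15 liver panel detects neither. The at-least-weekly monitoring that Table 3 prescribes for moderate diarrhea begins only once someone knows the diarrhea is there. What is at stake is the completeness, grading and dating of symptomatic AEs, and how soon staff learn of them.

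**Working it through.** **Inputs**

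- Cycle length: treatment is given "for continuous 28-day cycles" (section 5.1).
- Windows: ±3 days on C1D8, on day 1 of cycles after the first, and on the day 15 visits; none is shown for C1D1 (Table 1).
- Patients: 34 (section 14).

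**The rows side by side**

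| Contact in Table 1 | What is done there | Both toxicity rows |
|---|---|---|
| C1D1 (first dose) | full visit | marked |
| C1D8 | ECG | blank |
| C1D15, C2D15, C3D15 | liver panel | blank |
| Day 1 of each later cycle | full visit | marked |
| End of Treatment | full visit | marked |

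Footnote A and section 9.3 agree with the blank cells, so these are not an artefact of how the table was read.

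**Gaps as planned**

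- First dose to first later inquiry: 28 days nominal; 28 − 3 = 25 to 28 + 3 = 31 with the window.
- Between later day-1 visits: 28 days nominal; up to 28 + 3 + 3 = 34.

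**Gaps if the four contacts are used**

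- First dose to first later inquiry: 7 days nominal; 4 to 10 with the window.
- Cycle 1 gaps are 7, 7 and 14 days, so the longest falls from 28 to 14 nominal (at most 14 + 3 + 3 = 20).
- Cycles 2 and 3: two gaps of 14 days replace one of 28.

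**Mean lag from onset to the next inquiry.** Assume onset is uniform over a 28-day cycle. The documents give no onset distribution, so this is only illustrative. Mean lag = (sum of squared gaps) / (2 × 28).

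- As planned: 28² / 56 = 14.0 days.
- Cycle 1 with C1D8 and C1D15 used: (7² + 7² + 14²) / 56 = 294 / 56 = 5.25 days.
- Cycles 2 and 3 with day 15 used: (14² + 14²) / 56 = 392 / 56 = 7.0 days.

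**Volume.** 4 contacts × 34 patients = 136, if every patient attends all four.

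**Effect on the design figures.** Section 14 states a type I error of 0.075 and power of about 80%. An exact binomial rule with 31 evaluable patients (34 less about 10%), success if at least 20 are not removed, and rates of 0.50 and 0.70 gives 0.0748 and 0.808. With 34, a cut-off of 22 gives 0.0607 and 0.807. Whether 31 or 34 is meant is a separate matter. The inputs are the number of patients, the cut-off and the two rates. The solicitation schedule is not among them, so the proposed change leaves these figures alone.

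**The case against.** The strongest reply is that the trial's decision does not turn on how often patients are asked. Section 14 tests the proportion not removed for toxicity or intolerance, and the stopping guideline in 14.1 counts removals. A removal is known when it happens, and a patient who stops early is asked at End of Treatment. This stands. A reader might infer that sparse solicitation undermines the stopping guideline or the primary test; the documents do not support that.

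Three other tempting inferences also fail.

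- *Toxicity clusters early.* Section 10.5 says "These findings were generally observed within the first 12 weeks of treatment", but that sentence describes ALT and AST elevations, which the day 15 panel measures. For symptoms, the same section says diarrhea can occur at any time and gives pneumonitis onset from under 1 to 15 months.
- *Most patients have something to miss.* Table 5 reports diarrhea in 47% (grade 3 or higher in 14%) and pneumonia terms in 25% (16%). It gives no onset times, durations or overlap, so it cannot show how many events fall wholly between two visits.
- *Continuous monitoring is contradicted.* The phrase can reasonably mean ongoing review of incoming reports. The calendar does not schedule anything more frequent, but that is not a contradiction.

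There is also cover between visits. Section 9.4 relies on standard medical practice and requires SAEs to be reported within 24 hours, and the Appendix B diary has a daily comments column. This reduces the gap without closing it: none of these schedules an inquiry, and the diary is free text, ungraded and collected at the end of the cycle.

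Finally, days 8 and 15 carry only an ECG or a blood draw, and the documents do not say that patients see study staff then. That is fair, and it is why the change must allow a telephone call.

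**Conclusion.** The point holds as a low-cost improvement to AE capture. For a patient who remains on drug, no symptom inquiry is scheduled between the first dose and C2D1, 28 days later (25 to 31), and later gaps can reach 34 days, while four contacts in the first three cycles go unused for this purpose. The consequence is less complete, less well graded and less well dated symptomatic AEs, recognised later than they need be, in a trial whose primary objective is to describe toxicity.

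The size of the loss in events cannot be derived from the documents; only the timing can. The removal-for-toxicity decision, type I error and power are largely unaffected, and liver toxicity is already measured at day 15. The conclusion assumes that the day 8 and day 15 contacts take place as scheduled. The mean-lag figures assume uniform onset.

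**What to change.** In Table 1, mark the toxicity assessment and solicited AE rows at C1D8, C1D15, C2D15 and C3D15. Extend footnote A to those days, and amend the solicitation wording in section 9.3 to match. Allow the inquiry to be made by telephone when the patient does not see study staff that day.

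The cost is a few minutes of coordinator time per contact (an estimate), for up to 136 contacts. Where the ECG or blood draw is done away from study staff, the call is a new contact. Somewhat more low-grade AEs will be recorded. No visit, test or procedure is added, and no dose or stopping rule changes.

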7. DOSING DELAYS/DOSE MODIFICATIONS

Please refer to table 2 below.

Patients who experience a Grade 2 or 3 toxicity and recover to \leq Grade 1 (or to pretreatment baseline level of toxicity) may continue treatment at the next lower dose level (i.e., Dose level 2 down to dose level 1).

Once the dose has been reduced, patients must remain at the reduced dose for 28 days. Dose escalation may occur at the discretion of the investigator and may occur every 28 days. Patients may have their dose de-escalated from level 2 to level 1, three times before being removed from treatment.

Please note:

- There are no dose escalations above 150 mg BID
- There are no dose reductions below 100 mg BID

Table 2

Dose Modification Schedule	
Dose Level	Dose of Zydelig
Level 2 (starting dose)	150 mg PO BID
Level 1	100 mg PO BID

Table 3

Dose Modifications for Toxicities Due to Zydelig

Pneumonitis	Any symptomatic pneumonitis		
	Discontinue Zydelig in patients with any severity of symptomatic pneumonitis		
ALT/AST	>3.0-5.0 x ULN	>5-20 x ULN	>20 x ULN
	Decrease Zydelig to 100 mg BID and monitor weekly until ≤ 1 x ULN.	Withhold Zydelig. Monitor at least weekly until ALT/AST are ≤ 1 x ULN, then may resume Zydelig at 100 mg BID.	Discontinue Zydelig permanently.
Bilirubin	>1.5-3 x ULN	>3-10 x ULN	>10 x ULN

	Decrease Zydelig to 100 mg BID. Monitor at least weekly until ≤ 1 x ULN.	Withhold Zydelig. Monitor at least weekly until bilirubin is ≤ 1 x ULN, then may resume Zydelig at 100 mg BID.	Discontinue Zydelig permanently.
Diarrhea*	Moderate diarrhea	Severe diarrhea or hospitalization	Life-threatening diarrhea
	Decrease Zydelig to 100 mg BID. Monitor at least weekly until resolved.	Withhold Zydelig. Monitor at least weekly until resolved, then may resume Zydelig at 100 mg BID.	Discontinue Zydelig permanently.
Neutropenia[^]	ANC 1.0 to <1.5 Gi/L	ANC 0.5 to <1.0 Gi/L	ANC <0.5 Gi/L
	Maintain Zydelig dose.	Decrease Zydelig to 100 mg BID. Monitor ANC at least weekly.	Interrupt Zydelig. Monitor ANC at least weekly until ANC ≥ 0.5 Gi/L, then may resume Zydelig at 100 mg BID.
Thrombocytopenia	Platelets 50 to <75 Gi/L	Platelets 25 to <50 Gi/L	Platelets <25 Gi/L
	Maintain Zydelig dose.	Decrease Zydelig to 100 mg BID Monitor platelet counts at least weekly.	Interrupt Zydelig. Monitor platelet count at least weekly. May resume Zydelig at 100 mg BID when platelets ≥ 25 Gi/L.
Pneumocystis pneumonia	Any symptomatic pneumonia		
	Discontinue Zydelig in patients with any severity of PCP		
CMV viremia/infection	Any CMV viremia/infection		
	Discontinue Zydelig in patients with any CMV viremia/infection		
Abbreviations: ALT, alanine aminotransferase; AST, aspartate aminotransferase; BID, twice daily; PCP, pneumocystis pneumonia; CMV, cytomegalovirus; ULN, upper limit of normal			

*Moderate diarrhea: increase of 4–6 stools per day over baseline. Severe diarrhea: increase of ≥ 7 stools per day over baseline.

[^] G-CSF might be administered at the discretion of the investigator

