3. PATIENT SELECTION

3.1. Eligibility Criteria

3.1.1. Inclusion Criteria (must meet all)

1. Histologically documented (by HPI or pathology report) iNHL as defined by follicular lymphoma (FL), marginal zone lymphoma (MZL), lymphoplasmacytic lymphoma/Waldenstrom disease (LPL/WM) and small lymphocytic lymphoma (SLL) or tiNHL as defined by large B cell transformation of any of the above entities including chronic lymphocytic leukemia (CLL)
2. Patients must be eligible to undergo high dose chemotherapy (HDT) followed by ASCT as a form of remission consolidation
3. Patients without evidence of documented disease progression clinically or radiographically after ASCT (stable disease (SD), partial remission (PR) or complete remission (CR)) who have had count recovery (ANC > 500 cells/mm³, non-transfused platelet count > 20,000 K/mm³) and are at least 30 days post ASCT but no more than 120 days post ASCT

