3.1.3. Age >18

3.1.4. ECOG performance status <4 (see Appendix A).

3.1.5. Life expectancy of greater than four months.

3.1.6. Patients must have normal organ function as defined below (after the HDT/ASCT):

- total bilirubin \leq 2x institutional upper limit of normal
- AST(SGOT)/ALT(SGPT) <2.5 X institutional upper limit of normal
- Creatinine \leq 1.5x institutional upper limit of normal OR creatinine clearance \geq 60 mL/min/1.73 m² for patients with creatinine levels \geq 1.5x upper limit of normal.

3.1.7. Because the effects of Zydelig on the developing human fetus are unknown, women of child-bearing potential and men must agree to use adequate contraception (hormonal or barrier method of birth control; abstinence) prior to study entry and for the duration of study participation. Female subjects of childbearing potential should have a negative pregnancy test within 72 hours prior to receiving the first dose of Zydelig. Male subjects must agree to use an adequate method of contraception starting with the first dose of the study drug Zydelig. Female and male participants must agree to use contraception for at least 30 days after the last dose of Zydelig. Women of childbearing potential is defined as women who continues to have menstrual periods, have not had a tubal ligation, or the removal of fallopian tubes, ovaries or uterus.

3.1.8. Ability to understand English and the willingness to sign a written informed consent document.

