3.2. Exclusion Criteria

- 3.2.1 Patients who have had chemotherapy or radiotherapy within 2 weeks of first dose of Zydelig.
- 3.2.2 Patients receiving any other investigational agents within 30 days of receiving Zydelig
- 3.2.3 Patients who were previously exposed to Zydelig and experienced progression of disease.
- 3.2.4 History of allergic reactions attributed to compounds of similar chemical or biologic composition to Zydelig.
- 3.2.5 Patients with active and/or untreated CNS lymphoma will not be eligible.
- 3.2.6 Patients with inflammatory bowel disease.
- 3.2.7 Uncontrolled intercurrent illness including, but not limited to ongoing or active infection (defined as requiring systemic antibiotic treatment and fever within 48 hours of screening), symptomatic congestive heart failure (patients with NYHA score of III and above are excluded), unstable angina pectoris, cardiac arrhythmia, or psychiatric illness/social situations that would limit compliance with study requirements.
- 3.2.8 Women who are pregnant or nursing or plan to become pregnant or nurse during the course of the study.
- 3.2.9 Positive HIV status.
- 3.2.10 Patients with lack of count recovery as defined by ANC > 500 cells/mm³, non-transfused platelet count > 20,000 K/mm³.
- 3.2.11 Patients who are unable to swallow pills.
- 3.2.12 Patients with moderate to severe lung disease including:
 - Patients requiring O₂ supplementation
 - Patients unable to walk 50 feet without stopping to rest
 - Obstructive lung disease as defined by pre-transplant FEV₁ ≤ 60% of predicted.
 - Restrictive lung disease as defined by pre-transplant FVC < 60% of predicted.
- 3.2.13 Patients taking strong CYP3A4 inhibitors or inducers with Risk X (Avoid Combination) according to Lexicomp. Please see appendix C for more information.
- 3.2.14 Patients with active hepatic disease, liver cirrhosis, or known HBV/HCV infection.
- 3.2.15 Patients with de novo diffuse large B-cell lymphoma.

3.2.16 Patients with h/o PCP pneumonia or positive CMV viremia confirmed twice at least 1 day apart at screening.

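### Entry and start-of-drug limits overlap Table 3 action bands, and the CMV rules disagree, so a pre-dose state can trigger a toxicity action; Section 14 does not say how such cases are counted

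*Combined protocol and SAP*

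**What the plan says.** **Entry and start.** Section 3.1.1 requires count recovery, given as "ANC > 500 cells/mm³, non-transfused platelet count > 20,000 K/mm³", between 30 and 120 days after transplant. Section 5.1 repeats these floors as the condition for starting drug at 150 mg BID (level 2). Section 3.1.6 allows "total bilirubin \leq 2x institutional upper limit of normal" and "AST(SGOT)/ALT(SGPT) <2.5 X institutional upper limit of normal". Section 3.2.16 excludes "positive CMV viremia confirmed twice at least 1 day apart at screening".

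**Actions on drug.** Table 3 decreases the dose at platelets 25 to <50 Gi/L, ANC 0.5 to <1.0 Gi/L and bilirubin >1.5 to 3 x ULN. Below 25 Gi/L platelets the instruction is "Interrupt Zydelig. Monitor platelet count at least weekly. May resume Zydelig at 100 mg BID when platelets ≥ 25 Gi/L". After a hold for ALT/AST it says "Monitor at least weekly until ALT/AST are ≤ 1 x ULN, then may resume Zydelig at 100 mg BID", and the bilirubin row uses the same target. For CMV it says "Discontinue Zydelig in patients with any CMV viremia/infection". The laboratory rows are absolute values; only diarrhea is defined relative to baseline. The text of Section 7, by contrast, accepts recovery to the pretreatment baseline level.

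**Analysis.** Section 14 tests the proportion not removed for toxicity or intolerance (0.70 satisfactory, 0.50 or less not). Section 14.1 reports removals together with all toxicities by type and grade, and halts the study if removals convincingly exceed 50%. Neither section says how an abnormality present before the first dose is counted.

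**The concern.** This is a single-arm safety trial in patients whose marrow and liver are still recovering from high-dose therapy. If the criteria for starting drug and the criteria for acting on toxicity cover the same values, a patient's transplant state can be handled and recorded as a drug effect, and there is no control arm to show the difference. Two things are at stake: the by-grade toxicity tables, which would mix pre-existing and emergent abnormalities, and, to a lesser and more conditional extent, the removal proportion that decides whether the drug is acceptable and that drives the safety halt. Any error in the removal proportion would run against the drug.

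**Working it through.** **1. Entry range against Table 3 action range**

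The platelet floor is printed as 20,000 K/mm³. It is read here as 20 Gi/L because the synopsis defines engraftment at 20K/mm³.

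| Item | Eligible at entry | Table 3 action | Overlap |
|---|---|---|---|
| Platelets (Gi/L) | >20 | <25 interrupt; 25 to <50 decrease | >20 to <25 and 25 to <50 |
| ANC (Gi/L) | >0.5 | 0.5 to <1.0 decrease | essentially the whole band |
| Bilirubin (x ULN) | ≤2 | >1.5 to 3 decrease | >1.5 to 2 |
| ALT/AST (x ULN) | <2.5 | first action at >3.0 | none |
| CMV | excluded only if confirmed twice | any viremia: discontinue | a single unconfirmed positive |

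**2. Recovery targets**

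A patient eligible at bilirubin 2 x ULN, or ALT/AST just under 2.5 x ULN, must reach 1 x ULN to resume after a hold under Table 3. Section 7's own text would accept return to baseline. The two cannot both govern. The holds begin above 3 x ULN (bilirubin) and above 5 x ULN (ALT/AST), so this conflict concerns recovery after a genuine rise, not the baseline state itself.

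**3. CMV wording side by side**

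- 3.2.16: excluded at screening only if viremia is confirmed twice, at least 1 day apart.
- 5.2: off drug if PCR becomes detectable or CMV infection develops.
- 5.3: off drug if confirmed on two consecutive draws with a value ≥500 IU/mL, or documented CMV disease.
- Table 3: off drug for any viremia or infection.

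Table 1 schedules CMV PCR before treatment and on Cycle 1 Day 1. A patient eligible after one unconfirmed positive could meet Table 3 at the first on-study draw, yet not meet 5.3.

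**4. Routes from a pre-dose state to removal**

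- CMV: direct under Table 3.
- Platelets, ANC, bilirubin: no platelet or ANC row discontinues, and bilirubin does so only above 10 x ULN. Removal would need three de-escalations from level 2 to level 1, a hold that cannot end, or investigator judgement under 5.3.

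**5. The plan's design figures**

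Section 14 gives a type I error of 0.075 and about 80% power but no cutoff. With X the number removed and the rule to accept if X ≤ c:

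- n = 31, c = 11: P(X ≤ 11 | 0.5) = 0.0748; P(X ≤ 11 | 0.3) = 0.808. This reproduces the stated pair.
- n = 34, c = 12: P(X ≤ 12 | 0.5) = 0.061; P(X ≤ 12 | 0.3) = 0.807.

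Both cutoffs are inferred, so both are carried forward.

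**6. Sensitivity**

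Suppose k patients are removed because of a pre-dose state and the other n − k have a true 30% removal rate. Then P(accept) = P(Bin(n − k, 0.3) ≤ c − k).

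| k | n = 31, c = 11 | n = 34, c = 12 |
|---|---|---|
| 0 | 0.808 | 0.807 |
| 1 | 0.730 | 0.733 |
| 2 | 0.636 | 0.644 |
| 4 | 0.411 | 0.432 |

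The value of k is an assumption; the documents give no basis for it.

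**The case against.** The strongest reply is that the protocol already has the means to separate baseline from drug effect. Table 3 is headed as toxicities due to Zydelig, 9.1 gives an attribution scale, 9.3 asks about time course and other causes, and the expected events, including counts and transaminases, are graded at baseline. In addition, 5.3 requires confirmation much as 3.2.16 does, and 5.2 speaks of PCR becoming detectable, which reads as a new event. On those two texts a single screening positive would not by itself end treatment.

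Much of this stands. The means exist, and a careful investigator could use them. What is missing is any rule in Section 14 that uses them. Attribution between 30 and 120 days after transplant, without a control arm, is a judgement in which a possible relation needs only that the event may be related. The CMV reply depends on 5.2 or 5.3 prevailing over Table 3, and the documents do not say that either does.

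A reader might infer that patients who enter with low counts or raised bilirubin will be removed for toxicity, and that the design will therefore reject an acceptable drug. The documents do not support that. Those rows lead to a decrease or an interruption, and re-escalation, which the three-de-escalation route needs, is at the investigator's discretion after 28 days at the reduced dose. Nor do they support listing ALT/AST among the overlaps: a patient held above 5 x ULN has at least doubled from any eligible value.

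**Conclusion.** The contradictions are in the text. For platelets, ANC and bilirubin, a patient who meets every entry and start criterion can already be at a Table 3 action level, and the platelet floor of 20 Gi/L is below the resume level of 25 Gi/L. The recovery targets conflict with Section 7, and the CMV rules conflict among four places. This is more than missing detail, because the plan as written gives two instructions for the same patient.

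The consequence for the primary measure is narrower. It is direct only for CMV, and only if Table 3 governs; for counts and bilirubin it is indirect. The more certain effect is on the by-grade toxicity tables, where pre-existing abnormalities are not distinguished. The loss in the chance of acceptance, from about 0.81 to 0.73 with one baseline-driven removal and to 0.41–0.43 with four, shows how sensitive a trial of this size is. It is not an estimate of what will happen. It rests on an inferred cutoff, an assumed number of such removals and a true 30% rate in everyone else. The point should be addressed because the conflicts are certain and the correction is cheap.

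**What to change.** 1. Reconcile 3.1.1, 3.1.6, 3.2.16, 5.1, 5.2 and 5.3 with Section 7 and Table 3, including Table 3's absolute recovery values against Section 7's baseline clause. The clinical team sets the levels; this review takes no position on which is right.
2. In Section 14, keep every removal for toxicity in the primary count. Add a pre-specified sensitivity analysis that excludes removals where the triggering laboratory or CMV value was already at the action level before the first dose and had not worsened in absolute value.
3. Tabulate laboratory toxicities as shifts from the pre-dose value, which Table 1 already collects.

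Worsening by one CTCAE grade should not be the sole criterion. A patient who starts in the lowest platelet band may have no higher non-fatal grade to move to, so a real drug-caused fall would go uncounted.

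The cost is amendment wording, adjudication of each removal against its pre-dose value, and one extra analysis. No new data are needed.
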